and tolerability of PZQ in monotherapy. Adult participants with asymptomatic *Plasmodium falciparum* infection will be randomly allocated to one of two study arms with 22 participants in a placebo arm and 22 in an intervention arm with PZQ 40mg/kg once-daily dosing for 3 days.

Study overview

Trial Design

Single-center, assessor-blinded, randomized, placebo-controlled trial

Population

Adult, male or female, aged ≥ 18 years with asymptomatic *Plasmodium falciparum* infection between 200-5000 parasites/ μ l

Intervention

Oral treatment with PZQ 40mg/kg/day administered as once-daily dose for 3 consecutive days.

Control

Placebo administered as once-daily dose for 3 consecutive days.

Outcome

Parasitemia undetectable by thick blood smear on D7 after the start of administration of study drugs

Aims

To assess efficacy of PZQ in asymptomatic participants with *Plasmodium falciparum* parasites

Objectives

Primary Objective:

- To assess the proportion of participants with microscopically-determined parasite clearance on D7 after administration of PZQ compared with placebo

Secondary Objectives:

- 1) To assess the proportion of participants with $\geq 90\%$ parasitemia reduction on D7 compared with baseline between PZQ and placebo study arms
- 2) To assess the time to microscopically-determined parasite clearance in the PZQ study arm compared with the placebo arm
- 3) To assess the safety and tolerability of PZQ 40mg/kg once-daily dosing for 3 days
- 4) To assess the time to qPCR-determined parasite clearance in the PZQ study arm compared with the placebo arm
- 5) To assess the qPCR-determined cure rate in the PZQ study arm compared with placebo at D7 after study drug administration
- 6) To assess and compare the baseline-adjusted parasite mass of participants in the PZQ study arm compared with participants in the placebo study arm

Exploratory Objectives:

To assess activity of PZQ on gametocyte carriage

Rationale for trial design and praziquantel

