To calculate the sample size, we estimated that only 10% of participants in the placebo group will have a parasitemia below the microscopic limit of detection on day 7 versus 50% in the intervention group. With a power of 80% and an alpha error of 5% and considering a ratio 1:1 (treatment versus placebo group), we need 20 subjects in the placebo group and 20 subjects in intervention group. Accounting for a possible dropout rate of 10% in each study arm the final sample size will require recruitment of a total of 44 subjects.

Endpoints and assessment methods

Primary endpoint:

Parasitemia undetectable by thick blood smear on D7 after the start of administration of study drugs

Assessment method: Light microscopy

All those needing rescue treatment according to the physicians' judgement before day 7 will be counted as treatment failures together with all positives at day 7.

Secondary endpoints:

1) Parasitemia reduction $\geq 90\%$ on D7 compared with baseline assessed by light microscopy of thick blood smears

Assessment method: Light microscopy

2a) Time to parasitemia level < 100 parasites/ μl in the PZQ 3-day treatment group versus placebo assessed by microscopy

Assessment method: Light microscopy

2b) Time to parasitemia level below microscopic limit of detection in the PZQ 3-day treatment group versus placebo assessed by microscopy

Assessment method: Light microscopy

3) Occurrence of adverse events (AEs) in the PZQ 3-day treatment group versus placebo

Assessment method: Clinical examination and laboratory analysis

4) Time to parasite clearance assessed by qPCR in the PZQ 3-day treatment group versus placebo

Assessment method: Quantitative PCR

5) Parasitological cure rate assessed by qPCR on D7 after administration of study drugs

Assessment method: Quantitative PCR

6) Area under the curve (AUC) of microscopically-determined parasite mass between D0 and D7 in the PZQ 3-day treatment group versus placebo

Assessment method: Light microscopy

Exploratory endpoints

Proportion of participants with detectable gametocytes during D3-D7 in the treatment group versus placebo

Assessment method: Light microscopy

Duration of the study

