Participants will not benefit directly from participation in this study. The only benefits for the participants will be information about their general health status and the treatment from the *Plasmodium falciparum* infection in the end of the follow up. However, it is hoped that the information gained from this study will contribute to the development of safe and effective antimalarial drug. Compensation for missed working day if any and transportation fee for follow-up visit will be reimbursed.

Recruitment and withdrawal of trial participants

Participants

The study is designed as a randomized placebo-controlled assessor-blinded clinical trial to assess the safety and efficacy of praziquantel to treat *Plasmodium falciparum* infections in asymptomatic subjects in an endemic area of Gabon. Potential adult participants living in CERMELE's catchment areas in Gabon will be screened for parasitemia of 200 to 5000 pf/μl without malaria signs for inclusion into the clinical trial.

Informed Consent

All participants will sign and date the informed consent form before any study specific procedure is performed. At the screening visit, the volunteer will be fully informed of all aspects of the trial, the potential risks and their obligations. The following general principles will be emphasized:

- Participation in the study is entirely voluntary
- Refusal to participate involves no penalty or loss of medical benefits
- The participant may withdraw from the study at any time
- The participant is free to ask questions at any time to allow him or her to understand the purpose of the study and the procedures involved

The aims of the study and all tests to be carried out will be explained. The volunteer will be given the opportunity to ask about details of the trial and will then have time to consider whether or not to participate. Potential participants will be asked to sign and date two copies of the consent form, one for them to take away and keep, and one to be stored in the Investigator's File. These forms will also be signed and dated by the Investigator.

Inclusion Criteria

The subject must satisfy all the following criteria to be eligible for the study:

- Subject male or female with age ≥ 18 years
- *Plasmodium* parasitaemia with 200 to 5000 parasites/ μL

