Participants fulfilling all inclusion/exclusion criteria will be randomly allocated to receive either placebo once-daily dosing for 3 days, or PZQ 40mg/kg once-daily dosing for 3 days. The allocation ratio is 1:1. Randomization lists will be created using permuted blocks. Treatment allocation codes will be stored in opaque-sealed envelopes on whose surface is a pre-defined allocation sequence number. Each time a participant fulfils the inclusion criteria the opaque-sealed envelope with the next allocation sequence number is opened by the pharmacist or his delegate. During the treatment period all participants will be hospitalized for three days. Study procedures during the treatment period and follow-up visit will be the same in the two study arms.

Study procedures

Blinding

Laboratory investigators processing and analysing biological samples will be blinded to group allocation. The unblinded pharmacist or designate will prepare the treatment assigned by the randomization system and complete the corresponding treatment record form. Subsequently, verum and placebo will be administered by a physician who is not involved in diagnostic and analytic processes of the study. Other study physicians and study participants will be unaware of group allocation. Only the pharmacists and the physician administering verum and placebo know the group allocation. Verum and placebo are similar but not identical and will be administered to each participant separately out of the original packaging without changing labels.

Procedures will be performed at the time points indicated in the schedule of procedures (Table 2). Additional procedures or laboratory tests may be performed at any time, at the discretion of the investigators if clinically necessary.

Ascertainment of basic demographic information, clinical and past medical history

- Full medical history
- Prior concomitant medication
- Demographic data (gender, age)
- Clinical examination (including measurement of height and weight)
- Vital signs (including pulse, blood pressure and body temperature)

Blood sampling and laboratory tests

A series of blood samples will be drawn to perform different tests. Types of tests to be performed include molecular biology, biochemistry, haematology and parasitology.

Details of these tests are as follows:

Parasitology:

These tests include thick and thin blood smears and qPCR to detect the malaria parasite.

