- **Thick and thin blood smears** are prepared at screening. During the treatment period (D0, D1 and D2) thick and thin blood smears are prepared 6-hourly. Between D3 and D7 thick and thin blood smears will be prepared once daily. While thick blood smears will be used for quantification of parasitemia, thin blood smears will be used for determination of *Plasmodium* species.
- **Blood in RNA later (for qPCR)** is sampled at the same time as thick and thin blood smears. It is sampled at screening and during the treatment period (D0, D1 and D2) blood in RNA later it is sampled 6-hourly. Between D3 and D7 blood in RNA later will be sampled once daily.

Hematology, biochemistry tests:

These tests include full blood count, aspartate aminotransferase (AST), alanine aminotransferase (ALT), alkaline phosphatase, gamma-glutamyl transferase (GGT), total bilirubin, conjugated bilirubin, albumin, lactate dehydrogenase (LDH), creatinine, urea, glucose, sodium, potassium, calcium, and magnesium. These tests will be performed at screening, D3 and D7.

Urine sampling

- **Urine β -HCG test in female participants:** This is performed at screening to rule out any potential pregnancy at the beginning of the trial.

Administration of praziquantel

Participants allocated to the PZQ intervention group will receive PZQ orally on D0 once that the presence of all inclusion criteria and the absence of all exclusion criteria are secured. The dose will be 40 mg/kg once-daily for 3 days. Also, placebo will be administered orally, once daily for 3 days. To increase PZQ plasma levels study drugs will be administered with a standardised meal (40,42,43). Co-administration with food will also help to mask the taste of PZQ, thereby making it more similar to placebo and reducing the chance of reporting bias.

Clinical visits

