Generally, 'ULN = Upper Limit of Normal' and 'LLN = Lower Limit of Normal' are given to grade adverse events. Thereby usage of different blood value units in different laboratories can be largely respected. In the rare case that international grading classification systems used only one specific blood value unit (which might not be used in a given laboratory) investigators are asked to do the following: convert the result as given by your local laboratory to a result (and unit) which is required to adequately grade the abnormal laboratory value. Afterwards grade the adverse event based on the converted result by using adequate tables below. This approach will ensure timely grading of adverse events. Any method/source deemed appropriate by expert study staff can be used for conversion.

Statistics

Data analysis will consist of descriptive summaries for treatment groups. The primary endpoint of successful clearance of *Plasmodium falciparum* infection on Day 7 will be assessed for each patient and the number and percent of participants achieving this endpoint summarised for each group. Chi-square tests will be used for hypothesis testing between study groups.

For secondary endpoints descriptive summaries and plots over the time course for both individual patient results and groups will be presented. Where appropriate numbers and percent of participants achieving the given endpoint will be presented per group. Where appropriate highly skewed data will be log-transformed and presented as geometric means with 95% confidence intervals. Time to event data will be described using the Kaplan-Meier method and if appropriate by Cox proportional hazards models. Area under the curve (AUC) will be computed using the trapezoidal rule.

Quality control and quality assurance procedures

Monitoring

Monitoring will be performed according to ICH Good Clinical Practice (GCP) by a monitor who is independent from the study. The monitor will verify that the clinical trial is conducted and data are generated, documented and reported in compliance with the protocol, GCP and the applicable regulatory requirements. The investigators will provide direct access to all trial related source data/documents and reports for the purpose of monitoring and auditing by the sponsor and inspection by local and regulatory authorities.

Medical monitor

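### Secondary objective 6 calls for baseline-adjusted parasite mass, but endpoint 6 is a D0-D7 AUC defined without baseline; the cost is precision and exposure to chance imbalance, not bias

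*Protocol*

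**What the plan says.** **Objective.** Item 6 of the secondary objectives, in the Synopsis and again under Objectives, is "To assess and compare the baseline-adjusted parasite mass of participants in the PZQ study arm" compared with the placebo arm.

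**Endpoint.** Item 6 under Endpoints and assessment methods, and in the Synopsis, is "Area under the curve (AUC) of microscopically-determined parasite mass between D0 and D7 in the PZQ 3-day treatment group versus placebo". Baseline is not mentioned.

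**Analysis.** The Statistics section says "Area under the curve (AUC) will be computed using the trapezoidal rule". For secondary endpoints in general it adds "Where appropriate highly skewed data will be log-transformed and presented as geometric means with 95% confidence intervals". It names no covariate, ratio to baseline or between-arm model for the AUC.

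**Context.**
- Under Participants, volunteers "will be screened for parasitemia of 200 to 5000" parasites/µL.
- Under Allocation of the groups, "Randomization lists will be created using permuted blocks"; no stratification factor is given.
- Under Blood sampling and laboratory tests, "During the treatment period (D0, D1 and D2) thick and thin blood smears are prepared 6-hourly", then once daily from D3 to D7.
- Endpoint 1, by contrast, is tied to baseline in its own definition: a reduction of at least 90% "on D7 compared with baseline assessed by light microscopy of thick blood smears".

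**The concern.** The objective names a property, adjustment for baseline, that the definition of its endpoint drops. The protocol does write baseline into an endpoint when it means to, as endpoint 1 shows. Someone analysing endpoint 6 from the protocol must therefore either follow the endpoint and leave the objective unanswered, or follow the objective and choose an adjustment. The choices are not equivalent: AUC divided by baseline, change from baseline and ANCOVA can give different answers. An open choice can end up being made after the data are seen.

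Endpoint 6 is also the only endpoint that uses all the serial smears as a continuous density. The others dichotomise D7 or time a threshold crossing. The protocol's background describes a mouse model in which parasitaemia fell only while praziquantel was given. It also describes children whose mean density went from 3249 to 711 parasites/µL while prevalence did not fall (81% and 86%). If activity is partial or transient, this endpoint could show it, so its precision is worth protecting.

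**Working it through.** **1. The plan's own figure.** The only sizing figure is for the primary endpoint: 10% against 50% clearance, 80% power, 5% alpha, 1:1. With a two-sided test and pooled variance:

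n = [1.96·√(2·0.3·0.7) + 0.842·√(0.1·0.9 + 0.5·0.5)]² / 0.4² = 19.4, so 20 per arm.

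This reproduces the protocol. Adding 10% gives 22 per arm and 44 in total, as stated. The AUC endpoint was never sized, so nothing below changes a figure in the protocol.

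**2. Spread of entry density.** 5000/200 = 25-fold. The protocol gives no distribution within this range, so two assumptions are shown.
- Log-uniform: SD of ln density = ln(25)/√12 = 3.219/3.464 = 0.929 (0.40 on log10).
- Uniform on the natural scale: with x = density/5000 on 0.04 to 1, mean ln x = −0.866 and mean (ln x)² = 1.300, so SD = √(1.300 − 0.866²) = 0.742.

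**3. Chance imbalance in geometric mean entry density.** The 95% limit is exp(1.96·SD·√(2/n)); the median absolute imbalance uses 0.674 in place of 1.96.

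| Assumption | n per arm | 95% limit | Median |
|---|---|---|---|
| Log-uniform | 22 | 1.73-fold | 1.21-fold |
| Log-uniform | 20 | 1.78-fold | 1.22-fold |
| Uniform | 22 | 1.55-fold | 1.16-fold |
| Uniform | 20 | 1.58-fold | 1.17-fold |

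An unadjusted AUC carries such an imbalance forward to the extent that entry level persists through the week. The H0 reading itself is not the route: for a flat profile its trapezoid weight is 3 h/168 h = 1.8%.

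**4. Share of log-AUC variance explained by entry density.** This was simulated on the protocol's smear times (6-hourly H0 to H66, then daily to D7). Assumptions not in the protocol: log-uniform entry density, log-linear individual profiles, smear error SD 0.5 on the natural-log scale, a detection limit of 5 to 50/µL, and a between-person SD of the daily log slope of 0.1 to 0.5. Mean slopes were set so that 10% (placebo) and 50% (PZQ) are smear-negative on D7. Power is for log AUC at 20 per arm.

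| Slope SD per day | Variance explained | Power unadjusted | Power adjusted |
|---|---|---|---|
| 0.1 | 0.90–0.95 | 22–45% | over 99% |
| 0.2 | 0.67–0.90 | 40–68% | at least 99% |
| 0.3 | 0.43–0.80 | 62–83% | 98–99% |
| 0.5 | 0.19–0.53 | 88–95% | 97–99% |

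**5. Effect on the confidence interval.** Adjustment multiplies the interval's width on the log scale by about √(1 − R²): √(1 − 0.20) = 0.89 at the low end and √(1 − 0.95) = 0.22 at the high end. The gain runs from modest to very large, and the protocol has no data to say where in that range this trial will fall.

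**The case against.** **The protocol never says the AUC is analysed unadjusted.** It names the variable and how it is computed, specifies no between-arm test for it, and states the adjustment in the objective. The model could sit in a statistical analysis plan that is not at hand. This stands as far as it goes: a reader might infer that a raw AUC comparison is planned, and the document does not support that. What remains is narrower. The protocol itself fixes the endpoint, and that definition leaves out what the objective requires. A later plan would have to resolve the mismatch, not just add detail.

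**Randomisation protects the comparison.** Correct. An unadjusted comparison is unbiased, and its confidence interval already reflects chance imbalance. A reader might infer that the result would be invalid; it would only be less precise.

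**The AUC need not mainly reflect entry density.** Also correct. A reader might take the 25-fold range to mean that it does, but the share falls to about 20% when trajectories differ widely.

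**Skew is already provided for.** Log-transformation is allowed where appropriate, which limits the pull of a few high-density participants. It does not adjust for baseline.

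**Other endpoints share the load.** Endpoint 1 is relative to baseline, and endpoint 2a (time to below 100/µL) uses the serial smears and can show partial effect. This limits the importance of the point but does not repair endpoint 6.

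**Adjustment needs more than one line.** The density criterion is applied at screening; H0 is a separate smear up to 24 hours later and could fall outside the range or be negative. Rescue treatment before D7 would also alter the curve. Both are fair and are taken up in the fix.

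**Conclusion.** The mismatch between objective 6 and endpoint 6 is plain in the text, appears in both the Synopsis and the body, and needs no assumption. Its consequence is lost precision and exposure to chance imbalance in one secondary comparison, without bias.

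The size rests on assumptions. The 95% limit of imbalance in geometric mean entry density is about 1.7-fold if density is log-uniform, and nearer 1.6-fold if it is uniform; a typical imbalance is about 1.2-fold. Baseline may explain roughly 20% to 95% of log-AUC variance. Adjustment raised power in every scenario tried, by a little where trajectories differ widely and by a lot where they are similar. The primary endpoint and the sample size are not touched. The point is worth correcting because the contradiction is easy to remove and the precision is almost free.

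**What to change.** Align endpoint 6 and the Statistics section with objective 6:

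- Define the endpoint as log10 AUC from D0 to D7, by the trapezoidal rule at actual sampling times.
- Compare arms by ANCOVA with log10 pre-dose density as covariate, and report the adjusted ratio of geometric mean AUC with its 95% CI. Dividing AUC by baseline is another reading of the objective, but on the log scale it forces a slope of 1, which ANCOVA estimates instead.
- State which smear is baseline, and what replaces H0 if it is negative (for example, the screening density or the mean of screening and H0).
- State a value for an all-negative series, for example a fixed fraction of the detection limit. A single positive smear that enters the AUC is enough to keep it above zero.
- State how smears taken after rescue treatment enter the AUC.

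The cost is a few sentences and a little more analysis work. The screening and H0 smears are already in Table 2, so no extra sampling is needed. The one real burden is that the zero-count rule must be fixed in advance.

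### The exploratory gametocyte endpoint ignores pre-dose carriage, so the comparison is unbiased but imprecise and hard to read as activity on carriage

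*Protocol*

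**What the plan says.** The exploratory objective (Protocol, Objectives) is "To assess activity of PZQ on gametocyte carriage". One endpoint serves it (Endpoints and assessment methods, Exploratory endpoints): "Proportion of participants with detectable gametocytes during D3-D7 in the treatment group versus placebo", assessed by light microscopy. The definition does not mention gametocyte status before dosing.

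Eligibility sets "parasitaemia with 200 to 5000 parasites" per microlitre. No inclusion or exclusion criterion concerns gametocytes. Allocation of the groups describes 1:1 randomisation in permuted blocks and names no stratification factor.

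On smears, the Parasitology paragraph says that they "are prepared at screening. During the treatment period (D0, D1 and D2) thick and thin blood smears are prepared 6-hourly", then daily from D3 to D7. It adds: "While thick blood smears will be used for quantification of parasitemia, thin blood smears will be used for determination of" the species. Reading for gametocytes is not mentioned there.

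Baseline is used elsewhere. Secondary endpoint 1 is a reduction from baseline, and secondary objective 6 is "To assess and compare the baseline-adjusted parasite mass of participants in the PZQ study arm" compared with placebo.

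**The concern.** Activity on carriage can take two forms: existing gametocytes are cleared, or new ones are prevented. The endpoint separates neither. Three quite different courses all score positive:

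- an entry carrier who stays positive to D7;
- an entry carrier who is positive on D3 and negative from D5;
- a non-carrier who first turns positive on D6.

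One positive among five daily smears is enough, so clearance inside the window is lost.

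With 22 per arm and no stratification stated, the arms may also differ by chance in how many participants entered with gametocytes, and that difference feeds directly into the endpoint. At stake are the precision and the interpretation of the trial's only gametocyte result. The smears that could supply the missing baseline are already on the schedule.

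**Working it through.** **Inputs.** From the protocol: 22 per arm, the endpoint definition, and five daily smears in D3-D7. The protocol states no figure for this endpoint and gives no rate of gametocyte carriage, persistence or new appearance, so there is no planned figure to reproduce. Assumed instead, for illustration only:

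- entry carriage *b* = 20-40%;
- persistence *q* (an entry carrier has at least one positive D3-D7 smear) = 90%;
- new positives among non-carriers *e* = 5%;
- as a less favourable case, *q* = 70% and *e* = 10%.

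All 22 per arm are taken to be evaluable.

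**1. Chance imbalance at entry.** The SD of the arm difference in carriage is √(2b(1−b)/22).
- b = 20%: √(2 × 0.2 × 0.8 / 22) = 12.1 points.
- b = 40%: √(2 × 0.4 × 0.6 / 22) = 14.8 points.

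With two independent binomial counts, the arms differ by 3 or more carriers in 34-44% of trials.

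**2. Raw standard error, no drug effect.** p = bq + (1−b)e and SE = √(2p(1−p)/22).
- b = 20%: p = 0.18 + 0.04 = 0.22; SE = √(2 × 0.22 × 0.78 / 22) = 12.5 points.
- b = 40%: p = 0.36 + 0.03 = 0.39; SE = √(2 × 0.39 × 0.61 / 22) = 14.7 points.

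**3. Stratified standard error, no drug effect.** Only the variance within strata remains: v = bq(1−q) + (1−b)e(1−e), and SE ≈ √(2v/22).
- b = 20%: v = 0.018 + 0.038 = 0.056; SE = 7.1 points.
- b = 40%: v = 0.036 + 0.0285 = 0.0645; SE = 7.7 points.

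Simulating the Mantel-Haenszel risk difference gives the same values (7.2-7.7).

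**4. With an effect: persistence falls from 90% to 50%.** The 40-point effect among carriers becomes 0.40 × b, which is 8 points (b = 20%) to 16 points (b = 40%) in the raw endpoint. By simulation the SE is about 12-14 points raw and 9-10 stratified. The stratified difference itself averages about 7-16 points. Power is about 11-20% for the raw chi-square test, 14-35% for the stratified test and 8-32% for carriers alone.

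**5. Less favourable rates (q = 70%, e = 10%), no drug effect.**
- b = 20%: p = 0.14 + 0.08 = 0.22, raw SE 12.5; v = 0.042 + 0.072 = 0.114, stratified SE 10.2.
- b = 40%: p = 0.28 + 0.06 = 0.34, raw SE 14.3; v = 0.084 + 0.054 = 0.138, stratified SE 11.2.

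The gain shrinks but does not vanish.

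**6. Is the raw comparison biased?** No. Exact enumeration of the 5% chi-square test over b = 10-50%, q = 90% and e = 5% or 15% gives rejection in 4.6-5.1% of trials under no effect. Over the same range, power to detect complete absence of gametocytes on praziquantel is 35-100%.

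**The case against.** A reader might go further and infer that the endpoint cannot show activity at all. The document does not support that. The comparator is a concurrent randomised placebo arm, entry carriage is balanced in expectation, and the type I error holds (step 6). The window opens after the last dose at H48, so a carrier who clears before D3 is scored negative and does count in the drug's favour.

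A reader might also infer that the endpoint mostly records who entered with gametocytes. That depends on rates the protocol does not give. Over the assumptions in step 6, entry carriers make up between 40% and 95% of placebo positives.

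It is fair to add that post-treatment prevalence against placebo is a legitimate quantity, and that adjusting an exploratory endpoint for baseline is often left to the SAP, which is not at hand. It is also true that stratifying reduces noise without undoing the dilution by non-carriers, and that power stays low either way (step 4).

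Two things survive. The definition and its any-positive D3-D7 window are fixed in the protocol, and stratification alone would not recover clearance that occurs inside that window. And the stated uses of the smears do not include gametocyte reading, so the protocol does not secure a pre-dose status on which to stratify.

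**Conclusion.** The point holds in a limited form. The endpoint is valid as a randomised comparison but imprecise, and it does not tell clearance from prevention. On the assumed rates, ignoring entry carriage raises the standard error from 7-8 to 12-15 points under no effect, and from about 9-10 to 12-14 points if persistence is cut to 50%. With 70% persistence and 10% new positives the contrast is about 10-11 against 12-14. All of these rest on assumed carriage, persistence and appearance rates. That pre-dose status is left out, and that within-window clearance is hidden, follows from the wording alone. Low priority: one exploratory endpoint, with no bearing on the sample size or the primary analysis.

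**What to change.** - State that the screening and H0 smears are read for gametocytes, and define pre-dose carriage from them.
- Make the overall between-arm comparison of D3-D7 positivity stratified by, or adjusted for, pre-dose carriage.
- Report descriptively, by arm, the proportion of pre-dose carriers still positive at D7 and the proportion of pre-dose non-carriers who become positive.

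No visit or blood draw is added. The cost is a change of wording and slightly more slide reading. The carrier subgroup would be small, about 4-9 per arm on the assumed rates (22 × 0.2 = 4.4; 22 × 0.4 = 8.8), so its results should be presented as description and not as a test.
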